## 2. OBJECTIVES

### 2.1. Primary Objectives

- To assess the rate of complete remission (CR) after induction therapy with the combination of “7+V” [vosaroxin and standard dose infusional cytarabine] for patients with newly diagnosed, previously untreated acute myelogenous leukemia (AML)

### 2.2. Secondary Objectives

- To further evaluate and the safety and tolerability of “7+V”
- To evaluate for the presence of minimal residual disease (MRD) remaining after “7+V” induction and/or re-induction
- To determine CR/ CRi rate after one and / or 2 cycles of “7+V” induction
- To determine time to neutrophil and platelet recovery following “7+V” induction
- To assess disease free survival (DFS) at 1yr of patients achieving CR / CRi after “7+V” induction
- To assess overall survival (OS) at 1yr of all patients receiving protocol defined therapy
- To determine correlation of pretreatment HSCT comorbidity index, AML-Score, and Wheatley Index scores with disease response, DFS and OS

### 2.3. Exploratory Objectives

- To describe the mutational burden of this cohort of AML patients
- To correlate genomic aberration with response rate, DFS, and OS
- To determine the number of patients treated with vosaroxin who eventually go to allogeneic HSCT

## 3. STUDY DESIGN

### 3.1. Overall Design and Plan

- Single-arm, open-label, phase II study of vosaroxin in combination with cytarabine in patients with newly diagnosed AML.
- Vosaroxin will be administered intravenously at 90 mg/m^2 on days 1 and 4. Cytarabine will be administered in standard fashion as a continuous infusion of 100 mg/m^2 daily on days 1-7.
  - Patients with evidence of residual leukemia on “Day 14 biopsy” following initial induction will be offered re-induction with intravenous vosaroxin at 70 mg/m^2 on days 1 and 4 in combination with continuous infusion cytarabine at 100 mg/m^2 daily on days 1-7.
- Two-stage design. Forty-one (41) patients will provide 80% power to detect a 20% increase in complete remission rates (from 40% to 60%) with a Type I Error rate of 5%. The design permits one interim look to examine evidence of futility after the first 17 patients are evaluable for response. If  $\leq 7$  patients achieve CR then the likelihood of reaching the goal endpoint of  $\geq 60\%$  remission would be diminished. In this case, the DSMB (consisting of a representative from the funding organization, the study chairs, a biostatistician, and participating investigator to be selected by the study chairs) will review the clinical data to determine the merits of continued enrollment. If  $> 7$  CRs are observed then the second stage will open automatically and increase enrollment to 41 patients.
  - Stage 1: First 17 patients who are evaluable for response prior to futility analysis
  - Stage 2: Patients 18-41 enrolled after futility analysis
- Likelihood-based assessment of the statistical evidence be used to determine the reliability of the data generated and will provide the option of adding one or two extension cohorts of 10 participants each if the initial trial results are inconclusive.

### 3.2. Duration of Study

- First potential date of Study Activation: Feb 01, 2016
- Accrual duration: 12 months
- First patient enrolled/treated: Mar 2016
- Last patient enrolled/treated: Feb 2017
- Completion of 12-month follow-up post enrollment: Feb 2018

## 4. SELECTION OF STUDY POPULATION

### 4.1. Inclusion Criteria

Patients meeting the following criteria will be eligible:

- Age  $\geq$  18 years of age
- Ability to provide informed consent
- Ability to tolerate intensive therapy with vosaroxin 90mg/m^2 and standard dose of cytarabine as per investigator discretion
- ECOG performance status 0-2 at time of study entry (Appendix A)
- Morphologically confirmed new diagnosis of AML in accordance with WHO diagnostic criteria (Appendix B)
- Patients who have received hydroxyurea alone or have previously received “non-cytotoxic” therapies for MDS or MPN (e.g., thalidomide or lenalidomide, 5-azacytidine or decitabine, histone deacetylase inhibitors, low-dose cytoxan, tyrosine kinase or dual TK/src inhibitors) will be allowed
- Renal function: Serum creatinine  $\leq$  2.0 mg/dL
- Hepatic enzymes (ALT, AST)  $\leq$  2.5 x upper limit of normal
- Total bilirubin  $\leq$  1.5 x upper limit of normal unless clearly related to Gilbert’s Disease, hemolysis or leukemic infiltrate
- For patients in **stage 1 (patients #1-#17)**.
  - $\geq$  55 years of age with AML of any risk classification, OR
  - 18-54 years of age with high-risk AML disease based on one of the following:
    - Antecedent hematologic disorder including myelodysplasia (MDS)-related AML (MDS/AML) and prior myeloproliferative disorder (MPD)
    - Treatment-related myeloid neoplasms (t-AML/t-MDS)
    - AML with FLT3-ITD
    - Myeloid sarcoma
    - AML with multilineage dysplasia (AML-MLD)
    - Adverse cytogenetics (defined as -5/-5q; -7/-7q; abnormal 3q, 9q, 11q, 20q, 21q or 17p; t(6;9); t(9;22); trisomy 8; trisomy 13; trisomy 21; complex karyotypes ( $\geq$  3 clonal abnormalities); monosomal karyotypes

- For patients in **stage 2 (enrolled patient #18 and beyond)**.
  - $\geq 55$  years of age with AML of any risk classification, OR
  - 18-54 years of age with intermediate or high risk AML as defined by NCCN risk assignment (Appendix C)

## 4.2 EXCLUSION CRITERIA:

### Stage I:

- Patients 18-54 years of age with “good risk” AML defined as the presence of t(8;21) , inv(16), or t(16;16) as diagnosed by morphologic criteria, flow cytometric characteristics, and rapid cytogenetics or FISH (*Patients with t(8;21), inv(16), t(16;16) who are unable to receive anthracycline based induction will be allowed to enroll provided the medical reason they are unable to receive anthracyclines is clearly documented and provided they fulfill all other eligibility and criteria*).

### Stage I and Stage II:

- Patients with Acute Promyelocytic Leukemia (APL) as diagnosed by morphologic criteria, flow cytometric characteristics, and rapid cytogenetics or FISH or molecular testing
- Any previous treatment with vosaroxin
- Concomitant chemotherapy, radiation therapy
  - For patients with hyperleukocytosis with  $> 50,000$  blasts/uL; leukopheresis or hydroxyurea may be used prior to study drug administration for cyto-reduction at the discretion of the treating physician. Hydroxyurea must be stopped 24 hours prior to initiation of protocol defined therapy.
- Active CNS leukemia
- Active, uncontrolled infection. Patients with infection under active treatment and controlled with antibiotics are eligible.
- Active, uncontrolled graft vs. host disease (GVHD) following allogeneic transplant for non-AML condition (e.g. MDS, lymphoid malignancy, aplastic anemia). Patients with GVHD controlled on stable doses of immunosuppressants are eligible.
- Known HIV seropositivity
- Any other medical, psychological, or social condition that may interfere with study participation or compliance, or compromise patient safety in the opinion of the investigator or medical monitor
- LVEF  $< 40\%$  as measured by echocardiogram or MUGA
- Women who are pregnant or breastfeeding
- Renal insufficiency requiring hemodialysis or peritoneal dialysis

## 5. STUDY PROCEDURES

(see Table 1: Study Calendar)

### 5.1. Screening

Eligibility requirements and signed informed consent should be obtained within 15 days prior to Induction 1, Day 1.

#### 5.1.1 TRIAL REGISTRATION

The Vanderbilt-Ingram Cancer Center (VICC) Multi-Institutional Coordinating Center (hereafter referred to as “the Coordinating Center”) will coordinate enrollment onto the study. Once the Coordinating Center confirms eligibility and approves enrollment onto the study, it will provide the sites with confirmation and assigned patient ID numbers.

#### 5.1.2 TRIAL REGISTRATION PROCESS

To enroll a patient onto the study, participating sites should submit the enrollment packet to the Coordinating Center for eligibility confirmation and enrollment prior to the initiation of protocol therapy.

The enrollment packet includes:

- Enrollment Form
- Eligibility Screening Worksheet
- Signed patient consent form
- Eligibility supporting documents such as pathology reports, laboratory tests, etc.

The enrollment packet should be submitted via secure email transfer or fax using the contact information listed below:

Attn: VICC Multi-Institutional Coordinating Center

[contact]

or

[contact]

The enrollment packet should be submitted to the Coordinating Center as early as possible to ensure timely patient registration. Same-day enrollments cannot be guaranteed.

Vanderbilt typically does not grant exceptions to eligibility criteria.

Once the Coordinating Center has confirmed eligibility, the site will be notified via email with assigned patient sequence number.

## 5.2. Treatment / Hematologic Recovery

The treatment period will include up to two cycles of treatment (Induction 1, Induction 2). In each cycle, the first day of study treatment will be considered day 1. Each cycle will include vosaroxin treatment on Days 1 and 4 and cytarabine on Days 1-7 followed by a variable interval required to achieve hematologic recovery defined as absolute neutrophil count (ANC) > 1000 cells/ $\mu$ L and platelets > 100,000 cells/ $\mu$ L. Hematologic recovery is expected to occur approximately 5 to 6 weeks after the first treatment day of each cycle. Each cycle will be a minimum of 14 days and a maximum of 8 weeks.

### 5.2.1. Induction 1

An early assessment of antileukemic activity (bone marrow biopsy or aspirate) will be performed at approximately Day 14 for the sole purpose of guiding treatment decisions. If the early treatment assessment indicates an ablated bone marrow with < 5% blasts, CBC will be examined as noted in the schedule of events thereafter to monitor for hematologic recovery.

If the early treatment assessment indicates residual leukemia ( $\geq$  5% blasts) and a second cycle is indicated in the judgment of the investigator, the investigator may initiate Induction 2 any date prior to Induction 1 day 57 (no later than 8 weeks after Induction 1, Day 1) if eligibility criteria are met. Bone marrow assessments may be repeated as necessary per standard of care (investigator discretion) to clarify or confirm a finding of residual leukemia. In the event that blasts are  $\geq$  5% blasts, but  $\leq$  10%, the investigator may choose to pursue an additional bone marrow biopsy at a future date prior to making decision on whether Induction 2 is warranted.

### 5.2.2 Induction 2

Induction 2 will not be necessary for all patients, but may be appropriate if the Induction 1 early treatment or hematologic recovery assessment indicates residual leukemia is present, and if a second cycle is indicated in the judgment of the investigator. Eligibility for Induction 2 requires that non-hematologic toxicity and abnormal laboratory values be resolved to grade  $\leq$  1, if assessed by the investigator as related to treatment and clinically significant. Recovery of ANC, hemoglobin/hematocrit, and/or platelet counts is not required prior to Induction 2.

### 5.2.3 Consolidation

Consolidation therapy is not defined by the protocol. Patients achieving CR/CRi will proceed with consolidation therapy and/or hematopoietic stem cell transplantation at the discretion of the treating physician in accordance with institutional practice.

### 5.3. End of Treatment

End of treatment procedures will be performed for all patients when study treatment is discontinued for any reason or another AML therapy is started, including conditioning regimens for transplantation. Every reasonable effort will be made to complete the procedures to prevent loss to follow up. A separate visit may not be required, and the procedures performed at the last visit may satisfy the required end of treatment procedures. Ongoing serious adverse events (SAEs) assessed by investigators as related to study treatment will be followed with reasonable effort until the event resolves, stabilizes, is considered irreversible, or the patient receives a new AML therapy or dies.

### 5.4. Follow-Up

At the end of treatment, the purpose of follow-up will be to document survival status for all patients and to document disease status for patients in continuing CR or CRi. Every reasonable effort must be made to obtain information about patient status. In the event of death, additional information will be obtained, such as the date of death, cause of death, date of last contact, and laboratory and bone marrow results to document disease status at the time of death, such as continuing remission, relapse, persistent or recurrent leukemia. Follow-up for all patients will be based on chart review and/or phone call every 3 months after completion of protocol defined therapy for one year.

**TABLE 1. Study Calendar**

Procedures	Screening	C1: induction		C1: response assessment Weekly until recovery or D57 (+/- 3d) j,k,l,m	C2: induction			C2: response assessment Weekly until recovery or D57 (+/-3d) j,k,l,m	EoT p
		D1	D4		Within 3 days of C2D1	D1	D4		
TESTS & OBSERVATIONS									
Informed consent a	X								
Vital signs b	X	X	X	X		X	X	X	
H&P b	X	X				X			
ECOG PS b	X	X		X		X		X	
Directed physical exam b			X	X	X		X	X	
Adverse event evaluation c		X	X	X	X	X	X	X	
Concomitant med review	X	X	X	X		X	X	X	
Vosaroxin d		X	X			X	X		
Cytarabine d		X				X			
LABS									
Echocardiogram e	X				X				
EKG f	X		X		X		X		
CBC with differential g	X	X	X	X		X	X	X	X
Blood chemistry h	X	X	X	X		X	X	X	
PT, PTT, INR, fibrinogen	X								
Serum pregnancy test i	X								
DISEASE ASSESSMENT									
Bone marrow aspirate and core j	X			X o				X	X
Molecular, cytogenetics, FISH k	X			X				X	X
Correlative laboratory studies l	X			X				X	X
Disease status/survival m				X				X	X
Comorbidities n	X								

Long Term Observations	Follow-up via telephone and/or chart review	
	6mo after diagnosis	12mo after diagnosis
Disease Status/Survival m	X	X
Allogeneic HSCT status	X	X

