#### 12.4. Definition of Endpoints Response for Interim Analysis.

Response for interim analysis will be defined as the best response prior to or on the day-84 bone marrow biopsy.

- Leukemia-free Survival (LFS or DFS) is defined as the time from complete remission to disease progression or death for any reason. Patients who are disease free and alive as of last follow-up will be censored at their last follow-up date.
- Event-free survival is defined as the time from start of therapy to progression or death for any reason. Patient progression-free and alive at last follow-up will be censored at their last follow-up date.
- Overall survival is defined at the time from start of therapy to death for any reason. Patients alive as of last follow-up will be censored at their last follow-up date.

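### Table 1's last disease-status contact comes too early for 1-year DFS, and the plan does not say whether Table 1 or the longer schedule in section 5.4 governs

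*Combined protocol and SAP*

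**What the plan says.** Section 2.2 lists the endpoint as "To assess disease free survival (DFS) at 1yr of patients achieving CR" (the objective goes on to include CRi). Section 12.4 sets the time origin: "Leukemia-free Survival (LFS or DFS) is defined as the time from complete remission to disease progression or death for any reason". It also sets the censoring rule: "Patients who are disease free and alive as of last follow-up will be censored at their last follow-up date".

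Three places then fix how long patients are followed, each from a different starting point:

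- Table 1, Long Term Observations: disease status and survival at 6 months and at "12mo after diagnosis", with nothing later. Footnote m repeats the 6- and 12-month contacts without naming the anchor. It refers to section 3.1, which contains no follow-up schedule.
- Section 5.4: chart review or phone call "every 3 months after completion of protocol defined therapy for one year".
- Section 3.2: 12 months of follow-up counted from enrollment, projected to finish in February 2018.

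On timing of response, section 5.2 states: "Hematologic recovery is expected to occur approximately 5 to 6 weeks after the first treatment day of each cycle".

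**The concern.** A 1-year DFS estimate needs some responders to be under observation 12 months after CR. A calendar that ends 12 months after diagnosis cannot provide this, because the weeks between diagnosis and CR come off the end of follow-up for every responder. Under the censoring rule in section 12.4, every event-free responder would leave the risk set before month 12.

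Section 5.4 could repair this, but nothing says it overrides Table 1. Section 5 itself sends the reader to Table 1, and transplant status, needed for an exploratory objective, is scheduled only there. The completion point that starts the section 5.4 clock is not defined. Whether a named secondary endpoint can be estimated therefore depends on which text a site uses, and sites may differ.

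**Working it through.** **The plan's own date.** Last patient enrolled February 2017 + 12 months = February 2018, as section 3.2 states. That date is consistent with 12 months from enrollment, not from CR.

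**Inputs.** Recovery, which CR requires, is expected 35 to 42 days after day 1 of a cycle (section 5.2). Induction 2 may start up to 8 weeks (56 days) after the first day of Induction 1 (section 5.2.1). The last response assessment in a cycle is day 57 plus 3 days (Table 1). The documents do not give the time from diagnosis to treatment. I assume 0 to 15 days, 15 being the eligibility and consent window in section 5.1. One month is 30.44 days.

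**Formulas** (days counted from the first treatment day):

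- Observation after CR under Table 1 = 365 − (lag from diagnosis) − (day of CR).
- Observation after CR under section 5.4 = (day of completion) + 365 − (day of CR).

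**Days to CR.** One cycle: 35 or 42. Induction 2 starting on day 17, just after the day-14 marrow: 16 + 35 = 51 or 16 + 42 = 58. Latest case, Induction 2 at 56 days and assessment on its day 60: 56 + 59 = 115.

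| Scenario | Day of CR | Table 1, no lag | Table 1, 15-day lag | 5.4, completion = end of 7-day infusion | 5.4, completion = response assessment |
|---|---|---|---|---|---|
| One cycle, week 5 | 35 | 330 d (10.8 mo) | 315 d (10.3) | 7 + 365 − 35 = 337 d (11.1) | 365 d (12.0) |
| One cycle, week 6 | 42 | 323 d (10.6) | 308 d (10.1) | 7 + 365 − 42 = 330 d (10.8) | 365 d |
| Early Induction 2, week 5 | 51 | 314 d (10.3) | 299 d (9.8) | 23 + 365 − 51 = 337 d (11.1) | 365 d |
| Early Induction 2, week 6 | 58 | 307 d (10.1) | 292 d (9.6) | 23 + 365 − 58 = 330 d (10.8) | 365 d |
| Latest possible CR | 115 | 250 d (8.2) | 235 d (7.7) | 63 + 365 − 115 = 313 d (10.3) | 365 d |

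Every Table 1 figure is below 365 days. The sign does not depend on the assumed lag, since CR always follows diagnosis. The section 3.2 anchor, with enrollment taken as the first treatment day, gives the same values as the no-lag column.

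**Which reading of completion the text favours.** Section 5.2 describes each cycle as treatment "followed by a variable interval required to achieve hematologic recovery", so recovery belongs to the cycle. Section 5.4 opens with "At the end of treatment, the purpose of follow-up will be to document survival status for all patients". Footnote m treats the response assessment as part of therapy, and Table 2 bars other AML treatment until protocol therapy ends. These support the last column, but none of them is a definition.

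**If February 2018 were a hard end (28 February).** One-cycle responders still reach 12 months from CR if treatment started by 28 Feb 2018 − (365 + 35) d = 24 Jan 2017, or − (365 + 42) d = 17 Jan 2017. That covers about 10.8 or 10.6 of the 12 accrual months, so only late enrollees are affected.

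**Patients concerned.** 41 × 0.40 = 16.4 and 41 × 0.60 = 24.6, so about 16 to 25 patients in CR, with CRi adding to this.

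**The case against.** The strongest reply is that section 5.4 already gives a direct instruction. It applies to all patients, names disease status in continuing remission as its purpose, and on the favoured reading reaches 12 months from CR. The two schedules can both be met, so a site that stopped at the Table 1 column would be omitting a requirement. Table 1 sets no window for its long-term contacts, so a late chart review could capture later status. February 2018 is only a projection. The endpoint is also descriptive: with 16 to 25 patients and a proportion near 50%, the 95% interval would be about ±1.96 × √(0.25/25) = ±20 points to ±1.96 × √(0.25/16) = ±25 points even with full follow-up, and no decision rule uses it.

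Much of this stands. It makes the loss of the 1-year estimate conditional on sites working from Table 1, and it limits the importance. It does not remove the conflict. Section 5 directs sites to Table 1, no text sets an order of precedence, and late contacts would be chance rather than plan. Section 5.4 alone also falls short, at 313 to 337 days, if completion is read as the end of the infusion.

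**Conclusion.** The concern holds. If contacts follow Table 1 as written, DFS is observed for at most 10.6 to 10.8 months after a one-cycle CR at the expected time, and about 8 months after the latest possible CR. No responder is then at risk at month 12, and a 1-year Kaplan-Meier estimate does not exist unless the curve has already reached zero. If contacts follow section 5.4, with completion taken as the response assessment or end of treatment, the estimate is available.

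The figures rest on the recovery time in section 5.2, on contacts made at their nominal dates, and on an assumed lag of 0 to 15 days from diagnosis to treatment. The effect is limited: the primary CR endpoint is untouched, DFS to about 10 months remains estimable for responders at the expected recovery time, and section 5.4 covers 1-year OS, which is counted from the start of therapy. It should be corrected because the repair is small and the endpoint is a stated objective.

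**What to change.** 1. Make the Table 1 long-term columns, footnote m (including its pointer to section 3.1) and section 3.2 agree with section 5.4.
2. Define the completion point in section 5.4 as the response assessment or end of treatment.
3. For patients in CR or CRi, require the last chart or phone contact to fall on or after 12 months from the documented CR/CRi date.
4. Move the projected completion date. For a last patient starting 1 to 28 February 2017, CR at day 35 to 42 plus 365 days gives 8 March to 11 April 2018. The latest possible CR (day 115) gives 27 May to 23 June 2018. The projection becomes about April 2018, and up to about June 2018, which is 1 to 4 months later than stated.

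**Cost.** Protocol wording, plus remote contacts. Table 1 plans 2 × 41 = 82 contacts and section 5.4 plans 4 × 41 = 164, a difference of 82. Allowing one further contact for each of 16 to 25 responders gives at most about 98 to 107 more than Table 1, and fewer once deaths are counted. Against section 5.4 the addition is 0 to 1 per responder, at most about 16 to 25 in all.

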## Schedule of Assessments for VITAL STUDY

- a Informed consent must be obtained within 15 days prior to initiation of trial treatment
- b The screening physical examination, ECOG performance status, hematology, chemistry, PT/INR and serum pregnancy test must be conducted within 7 days from C1D1. If the initial examinations are obtained within 72 hours of C1D1, they do not need be repeated. At the baseline visit only, height will also be recorded. PEs and laboratory assessments will be

completed until count recovery as directed on calendar. Directed physical exams as per investigator discretion. Vital signs to include weight.

c Adverse event reporting will be required on days as noted in schedule of assessments. In the event that AEs occur between these visits, they will be captured if they meet criteria as defined in section 10.

d Vosaroxin is administered on D1 and D4 as per section 3.1. Oral cryotherapy will be utilized in association with Vosaroxin administration (see appendix E). Cytarabine will be administered via continuous infusion D1-D7.

e Echocardiogram will be conducted to assess cardiac function prior to administration of chemotherapy. In the event that there are abnormalities on the initial echocardiogram, or if the investigator has concern for cardiac complications during the first induction, a second echocardiogram may be conducted as per standard of practice.

f EKGs will be obtained during screening and again after vosaroxin administration on D4 visit.

g CBC with differential will include RBC, Hgb, hematocrit, total WBC, ANC, platelet count, and  $\geq$  5 part differential

h Chemistry panel includes the following: urea or BUN, creatinine, sodium, potassium, calcium, magnesium, phosphorus, glucose albumin, total protein, ALT, AST, total bilirubin, uric acid, and LDH

i A serum pregnancy will be performed only at baseline when appropriate as per protocol.

j Bone marrow biopsy and aspirate are required prior to enrollment. In the event that a diagnostic bone marrow aspirate/biopsy was performed prior to study-specific informed consent being obtained, diagnostics from this marrowing may be reported (and specimen collection at screening will be limited to biospecimens for lab correlates, see footnote L below). Bone marrow aspirate and biopsy also are required at the following time points:

- **C1D14 (+/- 2 days):** for assessment of residual leukemia. Patients with residual leukemia at this assessment are eligible for a second round of induction (C2).
- **During response assessment period (C1 and/or C2):** upon peripheral count recovery (as determined per weekly assessments); **OR** per investigator discretion, even in absence of count recovery; **OR** at EoT occurring no later than D57 (e.g., in absence of peripheral count recovery, or patient still being followed for inconclusive prior marrow). Note that marrow biopsy/aspirate is **NOT** required to be repeated as an EoT activity if already performed at recovery.

k Molecular (mutation testing) and cytogenetic (classic karyotyping testing  $\pm$  FISH) will be performed as per standard of care. These analyses should be reported at study enrollment and in setting of response assessment at recovery or EoT, per standard of care.

l Peripheral blood and aspirate from bone marrow will be required as per the laboratory manual at study enrollment and in setting of response assessment at recovery or EoT.

m Disease assessment and survival will be noted during therapy and at 6 and 12mo follow up, as per section 3.1. During therapy, disease assessment should be reported in setting of response assessment at recovery or EoT.

n Co-morbidities and risk stratification will be assessed prior to therapy via HCT-Comorbidity index, Wheatley index, AML-SCORE (see Appendix F), and then correlated with response to induction and rates of allogeneic hematopoietic stem cell transplant as per exploratory endpoints.

o At C1D14 (+/- 2 days), bone marrow required for assessment of residual leukemia. Otherwise, disease assessment procedures during *response assessment period* should be performed per footnotes J, K, L, and M.

p EoT activities required ONLY if disease assessment procedures not already performed in setting of count recovery during *response assessment period* (C1 and/or C2). See also footnote J, bullet point 2.

